9.6.2.2.7 TV 9 (Treatment Week 30)

The following procedures are to take place at this visit:

- Administer the Worst Itch NRS and evaluate against the Failure-to-Improve criteria (see [Section 11.1](#))
- For patients who MEET the Failure-to Improve criteria
 - Stop study medication
 - Perform End of Treatment Visit (TV14) procedures
- For patients who DID NOT meet Failure-to-Improve perform the following procedures
 - obtain vital signs
 - collect urine for pregnancy (must be confirmed negative prior to dispensing study drug)

- collect blood for PK
- perform brief neurological assessment
- perform 12-lead ECG after at least 5 minutes in a supine position (See the Study Reference Manual for ECG procedures, [section 17.4](#) Electrocardiograms for the handling of Cardiovascular adverse events)
- administer PRO measurements:
 - Average itch intensity NRS
 - VRS
 - ItchyQoL
 - MOS Sleep-R
 - HADS

The PRO questionnaires must be administered at the study site under the supervision of and by trained study staff, strictly adhering to PRO Administration Instructions (see Study Reference Manual).

- record AEs
- review of concomitant medications, including over-the-counter medications, nutritional supplements, and vitamins
- reinforce compliance
- perform study drug accountability, retrieve previously dispensed study drug
- dispense the study drug to the patient required until the next Treatment Visit

9.6.2.2.8 TV 10 (Treatment Week 34)

The following procedures are to take place at this visit:

- Administer the Worst Itch NRS and evaluate against the Failure-to-Improve criteria (see [Section 11.1](#))
- For patients who MEET the Failure-to Improve criteria
 - Stop study medication
 - Perform End of Treatment Visit (TV14) procedures
- For patients who DO NOT meet Failure-to-Improve perform the following procedures
 - obtain vital signs
 - collect urine for pregnancy (must be confirmed negative prior to dispensing study drug)
 - collect blood for PK
 - perform brief neurological assessment
 - perform 12-lead ECG after at least 5 minutes in a supine position (See the Study Reference Manual for ECG procedures, [section 17.4](#) Electrocardiograms for the handling of Cardiovascular adverse events)

- administer PRO measurements:
 - Average itch intensity NRS
 - VRS
 - ItchyQoL
 - MOS Sleep-R
 - HADS

The PRO questionnaires must be administered at the study site under the supervision of and by trained study staff, strictly adhering to PRO Administration Instructions (see Study Reference Manual).

- record AEs
- review of concomitant medications, including over-the-counter medications, nutritional supplements, and vitamins
- reinforce compliance
- perform study drug accountability, retrieve previously dispensed study drug
- dispense the study drug to the patient required until the next Treatment Visit

9.6.2.2.9 TV 11 (Treatment Week 38)

The following procedures are to take place at this visit:

- Administer the Worst Itch NRS and evaluate against the Failure-to-Improve criteria (see [Section 11.1](#))
- For patients who MEET the Failure-to Improve criteria
 - Stop study medication
 - Perform End of Treatment Visit (TV14) procedures
- For patients who DO NOT meet Failure-to-Improve perform the following procedures
 - obtain vital signs
 - collect urine for pregnancy (must be confirmed negative prior to dispensing study drug)
 - collect blood for PK
 - perform brief neurological assessment
 - perform 12-lead ECG after at least 5 minutes in a supine position (See the Study Reference Manual for ECG procedures, [section 17.4](#) Electrocardiograms for the handling of Cardiovascular adverse events)
 - administer PRO measurements:
 - Average itch intensity NRS
 - VRS
 - ItchyQoL
 - MOS Sleep-R

- HADS

The PRO questionnaires must be administered at the study site under the supervision of and by trained study staff, strictly adhering to PRO Administration Instructions (see Study Reference Manual).

- record AEs
- review of concomitant medications, including over-the-counter medications, nutritional supplements, and vitamins
- reinforce compliance
- perform study drug accountability, retrieve previously dispensed study drug
- dispense the study drug to the patient required until the next Treatment Visit

9.6.2.2.10 TV 12 (Treatment Week 42)

The following procedures are to take place at this visit:

- Administer the Worst Itch NRS and evaluate against the Failure-to-Improve criteria (see [Section 11.1](#))
- For patients who MEET the Failure-to-Improve criteria
 - Stop study medication
 - Perform End of Treatment Visit (TV14) procedures
- For patients who DO NOT meet Failure-to-Improve perform the following procedures
 - obtain vital signs
 - collect urine for pregnancy (must be confirmed negative prior to dispensing study drug)
 - collect blood for PK
 - perform brief neurological assessment
 - perform 12-lead ECG after at least 5 minutes in a supine position (See the Study Reference Manual for ECG procedures, [section 17.4](#) Electrocardiograms for the handling of Cardiovascular adverse events)
 - administer PRO measurements:
 - Average itch intensity NRS
 - VRS
 - ItchyQoL
 - MOS Sleep-R
 - HADS

The PRO questionnaires must be administered at the study site under the supervision of and by trained study staff, strictly adhering to PRO Administration Instructions (see Study Reference Manual).

- record AEs

- review of concomitant medications, including over-the-counter medications, nutritional supplements, and vitamins
- reinforce compliance
- perform study drug accountability, retrieve previously dispensed study drug
- dispense the study drug to the patient required until the next Treatment Visit

9.6.2.2.11 TV 13 (Treatment Week 46)

The following procedures are to take place at this visit:

- Administer the Worst Itch NRS and evaluate against the Failure-to-Improve criteria (see [Section 11.1](#))
- For patients who MEET the Failure-to Improve criteria
 - Stop study medication
 - Perform End of Treatment Visit (TV14) procedures
- For patients who DO NOT meet Failure-to-Improve perform the following procedures
 - obtain vital signs
 - collect urine for pregnancy (must be confirmed negative prior to dispensing study drug)
 - collect blood for PK
 - perform brief neurological assessment
 - perform 12-lead ECG after at least 5 minutes in a supine position (See the Study Reference Manual for ECG procedures, [section 17.4](#) Electrocardiograms for the handling of Cardiovascular adverse events)
 - administer PRO measurements:
 - Average itch intensity NRS
 - VRS
 - ItchyQoL
 - MOS Sleep-R
 - HADS

The PRO questionnaires must be administered at the study site under the supervision of and by trained study staff, strictly adhering to PRO Administration Instructions (see Study Reference Manual).

- record AEs
- review of concomitant medications, including over-the-counter medications, nutritional supplements, and vitamins
- reinforce compliance
- perform study drug accountability, retrieve previously dispensed study drug

- dispense the study drug to the patient required until the next Treatment Visit

9.6.2.2.12 TV 14 (End of Treatment Visit)

This visit applies to all patients who completed TV13; including patients who met Failure-to-Improve criteria at any Treatment Visit during the study.

For patients who DID NOT meet Failure-to-Improve criteria during the conduct of the study, this visit (TV14) takes place after the patient has completed study medication.

- For patients who entered the Treatment Period at Visit 1a, TV14 would take place during week 51; four (4) weeks after TV13, as these patients should complete 50 weeks of treatment prior to TV14
- For patients who entered the Treatment Period at Visit 1b see [Table 8](#) for information on when TV14 is to take place

The following procedures are to take place at this visit:

- obtain vital signs
- perform physical examination
- perform brief neurological assessment
- complete the PAS
- perform 12-lead ECG after at least 5 minutes in a supine position (See the Study Reference Manual for ECG procedures, [section 17.4](#) Electrocardiograms for the handling of Cardiovascular adverse events)
- collect blood for central laboratory (hematology and chemistry) and serum pregnancy test for central laboratory
- collect urine for urinalysis at the central laboratory
- collect blood for PK
- at select sites only, perform skin biopsy (optional). Obtain 3 samples (i.e., H&E, nerve fiber density (histology) and MOR/KOR density (histology, Western Blot)); see the Lab and Study Reference Manuals for details
- administer PRO measurements:
 - Worst itch NRS
 - Average itch intensity NRS
 - VRS
 - ItchyQoL
 - MOS Sleep-R
 - HADS
 - SOWS

The PRO questionnaires must be administered at the study site under the supervision of and by trained study staff, strictly adhering to PRO Administration Instructions (see Study Reference Manual).

- record AEs

- review of concomitant medications, including over-the-counter medications, nutritional supplements, and vitamins
- perform study drug accountability, final retrieval of any dispensed study drug
- retrieve the Dosing Diary
- Dispense the 14 Day SOWS packet, instruct the patient on how to complete the scales and to complete the scales daily for 14 days
- Schedule the patient for the Washout and Safety Follow-up Period Visit

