9.5 STUDY OVERVIEW

This is an open label safety and tolerability extension study for patients who have completed study TR03. Patients will either enter directly a drug Treatment Period (Worst Itch NRS greater than or equal to 5 (≥ 5)) or enter an extended screening period of a no-drug Observation Period (Worst Itch NRS less than 5 (<5)) based on their reported NRS scores on the first Visit (Visit 1a). For up to 12 extended screening weeks, patients in the no-drug Observation Period may also transition into the drug Treatment Period if their Worst Itch NRS increases to greater than or equal to 5 (≥ 5).

The total study duration for any individual patient will be up to 53 weeks. For patients who enter directly into the Treatment Period, the total amount of time on drug will not exceed 50 weeks. For patients who enter the Treatment Period from the Observation Period, the total amount of time spent in the combined two periods of the study cannot exceed 50 weeks. All patients who received drug treatment will have a 2-week Washout and Safety Follow-up period at the end of the dosing period, unless consent is withdrawn.

The total amount of time in the Observation Period cannot exceed 12 weeks. After 12 extended screening weeks, subjects not eligible for the Treatment Period are screen failed from the study. The study periods are summarized below in [Table 2](#).

Table 2: TR03ext Study Periods

Study Period	Study Weeks	Duration
Observation Period	
Patients who do not meet the criteria to start Treatment are followed in Observation Period visits for up to 12 extended screening weeks. During this time, the patient may meet criteria and become eligible to enter the Treatment Period. If the patient does not meet the criteria to enter the Treatment Period by the end of 12 extended screening weeks (OV12), participation in the study ends and the patient is screen failed.
	Up to 12 extended screening weeks

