Treatment Period	
For patient directly entering the Treatment Period as of Visit 1a, the Treatment Period begins with Study Week 1 (Visit 1a) and ends with Study Week 50
 
For patients entering the Treatment Period after being followed in the Observation Period, the number of weeks on treatment and the end of the Treatment Period varies; Table 8 calculates the Treatment Visit assignments for any patient entering the Treatment Period from the respective Observation Period visits.
 
The End of Treatment Visit will take place after the patient completes the last week of study drug.
	Up to 50 weeks
Washout and Safety Follow-Up Period	
The Washout and Safety Follow-up Period is two (2) weeks in duration.
 
For patients directly entering the Treatment Period as of Visit 1a and completing 50 weeks of study drug treatment, the Washout and Safety Follow-up Period should take place during weeks 51 and 52.
 
For patients entering the Treatment Period after being followed in the Observation Period, the number of weeks on treatment and the end of the Treatment Period varies; Table 8 calculates the Treatment Visit assignments for any patient entering the Treatment Period from the respective Observation Period visits. The Washout and Safety Follow-up Period will take place during the two (2) weeks after the patients completes the last week of study drug.
 
The Washout and Safety Follow-up Period Visit will take place in the week following the completion of the two (2) week Washout and Safety Follow-up Period.
	2 weeks

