9.6.2.2.1 TV 3 (Treatment Week 5)

The following procedures are to take place at this visit:

- Administer the Worst Itch NRS and evaluate against the Failure-to-Improve criteria (see [Section 11.1](#))
- For patients who MEET the Failure-to Improve criteria
 - Stop study medication
 - Perform End of Treatment Visit (TV14) procedures
- For patients who DO NOT meet Failure-to-Improve criteria, perform the following procedures
 - obtain vital signs
 - collect urine for pregnancy test (must be confirmed negative prior to dispensing study drug)
 - collect blood for PK
 - perform 12-Lead ECG after at least 5 minutes in a supine position (See the Study Reference Manual for ECG procedures, [section 17.4](#) Electrocardiograms for the handling of Cardiovascular adverse events)
 - perform brief neurological assessment
 - administer PRO measurements:
 - Average itch intensity NRS

- VRS
- ItchyQoL
- MOS Sleep-R
- HADS

The PRO questionnaires must be administered at the study site under the supervision of and by trained study staff, strictly adhering to PRO Administration Instructions (see Study Reference Manual).

- record AEs
- review of concomitant medications, including over-the-counter medications, nutritional supplements, and vitamins
- reinforce compliance
- perform study drug accountability, retrieve previously dispensed study drug
- dispense the study drug to the patient required until the next Treatment Visit

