9.6.3 Observation Period (Extended Screening Weeks 1-12)

Only patients with Visit 1a Worst itch NRS score of less than 5 (<5) (Visit 1a for these patients is considered OV1) should enter the Observation Period, which includes subsequent study visits OV 2-4 at approximately one month intervals over the next 12 extended screening weeks (See [Table 7](#)). While patients remain in the Observation Period, they will not be considered enrolled into the study, but as participating in an extended screening process until they are eligible for enrollment. Patients evaluated at OV 2-4 and who record Worst itch NRS greater than or equal to 5 (≥ 5), and are otherwise eligible, can immediately begin Visit 1b and transition into the Treatment Period.

For these patients, the sum of time in the Observation Period and Treatment Period will not exceed 50 weeks. As a result, both the Observation Period and Treatment Period will differ in length for different patients. To ensure that the total number of study weeks does not exceed 50 weeks, that all patients complete proper titration of study drug up to the assessment of TV 2 during Treatment Week 3, and that the final Treatment Period visit is always TV14, see [Table 8](#) for visit details. As such, visits during this period are not equivalent to Treatment Weeks. During the Observation Period, patients are participating in Extended Screening Weeks.

9.6.3.1 *Observation Visit 2 at Extended Screening Week 4 and Observation Visit 3 at Extended Screening Week 8*

The following procedures are to take place at this visit:

- administer the Worst itch NRS
 - If the Worst Itch NRS is less than 5 (<5), perform the following Observation Visit procedures at any time during the visit
 - obtain vital signs
 - record AEs
 - record concomitant medications
 - If the Worst Itch NRS is greater than or equal to 5 (≥ 5), transition the patient to the Treatment Period and conduct Visit 1b procedures (described in [Section 9.6.4](#)) on the same day as this visit. See [Table 8](#) for a summary related to future Treatment Period Visits.

9.6.3.2 *Observation Visit 4 at Extended Screening Week 12*

The following procedures are to take place at this visit:

- administer the Worst itch NRS
 - If Worst Itch NRS is less than 5 (<5), perform the following Observation Visit procedures at any time during the visit
 - obtain vital signs
 - administer the following
 - Average itch intensity NRS
 - VRS
 - ItchyQoL
 - MOS Sleep-R
 - HADS
 - record AEs

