	2	0 mg (AM dose) 30 mg (PM dose)	--	
TC#1	3-4	30 mg BID		
	5-7	Titrate patients to tolerability with dose increases of 30 mg BID. Maintain dose for at least 3 to 4 days up to next dose level	Reduce dose incrementally by 30 mg	NA
The highest possible titration dose by the end of Treatment Week 1 is 60 mg BID				
Week 2 ²	1-7	Continue incremental increase in dose and maintaining at each dosed level for 3 to 4 days	Reduce dose incrementally by 30 mg	If 30 mg BID is not tolerated within one week, discontinue subject
The highest possible titration dose by the end of Treatment Week 2 is 120 mg BID				
Week 3 ²	1-7	Continue dose increase	Reduce dose by 30 mg BID and maintain	If 30 mg BID is not tolerated within one week, discontinue subject
The highest possible titration dose by the end of Treatment Week 3 is 180 mg BID				
Week 4 ² (TC#2)	1-7	Maintain dose at highest dose level reached on Week 3 Day 7	Reduce dose reached on Week 3 Day 7 by either 30 or 60 mg and maintain	NA
Treatment Week 5 ⁴ up to Treatment Week 50 (TV3-TV 14)	1-7	Maintain dose from Week 4 through TV14 ^{5,6}	Patient may down titrate twice over remaining duration of study	Patient discontinued if a 3 rd time down-titration is needed.

¹The decision to enter the patient into the Titration Period is based on Worst Itch NRS score NRS ≥ 5 obtained from the patient on Visit 1a or 1b

²The titration decision will be made based on tolerance to study drug

³Tolerance level is unacceptable to either the patient and/or investigator.

⁴The number of Treatment Weeks prior to TV 14 will vary for patients previously in the Observation Period depending upon the number of weeks spent in the Observation Period. See [Table 8](#)

⁵The achieved dose attained as of the end of Treatment Week 4 will be maintained throughout the rest of the Treatment Period. This dose will be defined as the patient's "maintenance dose". Two dose reductions to the next lower allowed dose are permitted during Treatment Weeks 5 – 50 (e.g., a patient at 90 mg BID can be reduced to 60 mg BID). If a third dose reduction is needed, the patient should be discontinued from the study.

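### TV14 is dated to week 51 and to four weeks after a week-46 visit, and Table 3 doses through a visit meant to follow the end of drug

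*Protocol*

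**What the plan says.** All references are to Version 2.0 of the protocol.

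- **Timing of TV14.** For patients who enter treatment at Visit 1a, section 9.6.2.2.12 states: "TV14 would take place during week 51; four (4) weeks after TV13, as these patients should complete 50 weeks of treatment prior to TV14". The same section says that the visit follows completion of study medication. The preceding visit is headed "TV 13 (Treatment Week 46)" in section 9.6.2.2.11.
- **Dosing.** The last row of Table 3 (section 9.7.1) is labelled "up to Treatment Week 50 (TV3-TV 14)" and instructs "Maintain dose from Week 4 through TV14". Section 9.5 caps exposure: "the total amount of time on drug will not exceed 50 weeks".
- **Period labels.** Table 2 says that "the Treatment Period begins with Study Week 1 (Visit 1a) and ends with Study Week 50", but also puts the End of Treatment Visit after the last drug week. Section 9.6.3 says that "the final Treatment Period visit is always TV14".
- **Washout.** Section 9.6.5 puts the washout visit in week 53.
- **SOWS.** Section 9.7.8 starts daily completion at TV14. In the same paragraph it also ties the daily scale to the two weeks after the last dose. Section 9.6.2.2.12 hands out the 14-day packet at TV14; no earlier visit does so.
- **Failure to improve.** At the visit where drug is stopped, sites are told: "Perform End of Treatment Visit (TV14) procedures".

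**The concern.** A site needs one date for TV14 and one answer to whether the patient is still taking drug on that day. The week-51 date and the four-week interval give different dates. Table 3 and section 9.6.2.2.12 give different answers on drug status.

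TV14 supplies the last value for change from baseline in the itch scores and most other patient-reported outcomes, and it is also the value from which change during washout is measured. Worst itch NRS looks back 24 hours (section 9.7.7.1). A visit two or more days after the last dose therefore records no itch from a dosing day, and any itch that has already returned is missing from the washout change. The PK sample at TV14 has the same ambiguity.

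The SOWS packet has a practical consequence as well. If TV14 slips, the days lost are the first ones off drug. Sections 9.3 and 9.7.8 rely on the scale in that period to prompt patients with moderate symptoms to call the site.

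**Working it through.** **Convention.** Week w runs from day 7(w−1)+1 to day 7w, with day 1 the first dosing day. Section 9.6 sets visit windows of ±3 days, except for Visits 1a and 1b.

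**1. Can the stated date be reproduced?**
- Week 46 is days 7×45+1 = 316 to 7×46 = 322.
- Adding 28 days gives days 344 to 350. Week 50 is days 7×49+1 = 344 to 350. So every day of week 46 leads to week 50.
- Week 51 is days 351 to 357. From the first day of week 46 to the first day of week 51 is 351 − 316 = 35 days, which is five weeks.
- With TV13 and TV14 each three days late from a first-day-of-week start, TV14 falls on day 316 + 3 + 28 + 3 = 350, still in week 50.

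The week-51 date is therefore not reproduced from the four-week interval. Five weeks reproduces it. A five-week step has a precedent in the schedule: TV7 is week 21 and TV8 is week 26.

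**2. Which date fits the rest of the text?**
- Fifty completed weeks end on day 350, so a day-351 visit satisfies the stated reason in 9.6.2.2.12.
- Day 351 + 14 = day 365, which is in week 53 (days 365 to 371). This agrees with section 9.6.5.
- Day 344 allows only 49 completed weeks before the visit (343/7), and day 344 + 14 = day 358, which is in week 52.

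Week 51 is the date that fits.

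**3. Table 3.** Dosing through a week-51 visit runs to day 351 or later, beyond 50 × 7 = 350 days. Read literally, the instruction breaks the cap in section 9.5 and contradicts the off-drug visit in section 9.6.2.2.12.

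**4. Drug supply.** TV13 dispenses enough until the next visit plus 8 spare tablets (sections 9.6.2.2.11 and 9.7.1). A four-week count from day 316 ends on day 343. At 180 mg BID the spare tablets add 8/12 = 0.67 day (30 mg tablets) or 8/6 = 1.3 days (60 mg tablets), so they do not reach day 350. Dispensing whole bottles can add more.

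**5. Effect at TV14, with the last dose on day 350.** SOWS days missed = days since last dose − 1, because the scale is completed at TV14 itself.

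| TV14 day | Days since last dose | SOWS days missed, of first 14 |
|---|---|---|
| 351 (nominal) | 1 | 0 |
| 354 (+3 window) | 4 | 3 (3/14 = 21%) |

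On day 351 the 24-hour itch recall still covers day 350, the last dosing day. From day 352 it does not.

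**The case against.** The strongest reply is that the intent is plain. Section 9.6.2.2.12 gives week 51 and explains why, Table 2 puts the visit after the last drug week, and section 9.6.5 and the 53-week duration fit. This stands. A reader might infer that sites have no way to tell which date is meant. The documents do not support that, since the weight of the text is on week 51, off drug.

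Table 3 can also be read kindly, as dosing to the end of its Week 50 row with the cap in section 9.5 governing. That reading is available, but the words still say through TV14, and this is the table sites dose from. The description of TV14 as the final Treatment Period visit is a label and carries little weight.

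A reader might go further on three other points:

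- **The two dates can never meet.** Fixing both visits at the start of their weeks gives windows of days 341–347 and 348–354, which do not overlap. But if TV13 falls on days 320–322 and TV14 is three days late, TV14 lands on days 351–353. The nominal interval is wrong; no stronger claim is supported.
- **Up to 6 of 14 SOWS days (43%) are lost.** This needs TV14 on day 357, so it lets the visit fall on any day of week 51. That is a looser reading than the one behind the non-overlapping windows, and the two cannot be combined.
- **Failure-to-improve patients or the washout weeks add further contradictions.** Holding TV14 at the stopping visit is an explicit rule. Washout in weeks 51–52 agrees with washout after TV14 if TV14 opens week 51.

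It is also fair to say that on the nominal date almost nothing is lost, that lesion scores would hardly change in a few days, and that efficacy is only summarised descriptively.

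**Conclusion.** The error is real and small. Four weeks should be five, and Table 3 should not dose through TV14. The SOWS needs a single anchor, because the packet handed out at TV14 cannot cover days off drug that precede the visit.

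The size is days: 1 day off drug and no SOWS loss on day 351; up to 4 days off drug and 3 of 14 SOWS days with the +3 day window. Only end-of-treatment and washout secondary measures and early withdrawal monitoring are affected. The primary endpoint, treatment-emergent adverse events in Treatment Weeks 5–50, is not.

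The figures assume visits at the start of their named week and a last dose on day 350. Version 2.0 Appendix 1, with Tables 6 and 8, is not shown and may fix the TV14 day more closely, so nothing is concluded about patients entering at Visit 1b.

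**What to change.** Keep TV14 in week 51 and make the text agree:

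- In section 9.6.2.2.12, change the interval after TV13 from four to five weeks, and define TV14 as the day after the last dose (day 351).
- Dispense five weeks of drug at TV13.
- In Table 3, end dosing at the close of Treatment Week 50, before TV14.
- Record the date and time of the last dose.
- Hand out the SOWS packet at TV13 and, in section 9.7.8, start daily completion on the day after the last dose. For failure-to-improve patients, hand it out at the stopping visit. Early SOWS days are then kept even if TV14 runs late.
- Leave the week-53 washout visit and the 53-week duration as they are.

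Moving TV14 to week 50 instead is not advised: the visit would come after only 49 completed weeks, and the washout visit would move to week 52.

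The cost is a few text edits and handing out one packet a visit earlier. No visit or procedure is added.
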